9.1.2 Discontinuation from study

Discontinuation from study is when the participant permanently stops receiving the study treatment, and further protocol-required assessments or follow-up, for any reason.

If the participant agrees, a final evaluation at the time of the participant's study discontinuation should be made as detailed in the assessment table (refer to [Section 8](#)).

9.1.3 Lost to follow-up

For participants whose status is unclear because they fail to appear for study visits or fail to respond to any site attempts to contact them without stating an intention to discontinue from study treatment or discontinue from study or withdraw consent (or exercise participants' data privacy rights), the investigator must show "due diligence" by documenting in the source documents steps taken to contact the participant, e.g. dates of telephone calls, registered letters, etc. A participant should not be considered as lost to follow-up until due diligence has been completed or until the end of the study.

9.2 Withdrawal of informed consent and exercise of participants' data privacy rights

Withdrawal of consent/opposition to use of data and/or biological samples occurs in countries where the legal justification to collect and process the data is consent and when a participant:

- Explicitly requests to stop use of their data

and

- No longer wishes to receive study treatment

and

- Does not want any further visits or assessments(including further study-related contacts)

This request should be as per local regulations (e.g. in writing) and recorded in the source documentation.

Withdrawal of consent impacts ability to further contact the participant, collect follow-up data (e.g. to respond to data queries) and potentially other country-specific restrictions. It is therefore very important to ensure accurate recording of withdrawal vs. discontinuation based on the protocol definitions of these terms.

In this situation, the investigator should make a reasonable effort (e.g. telephone, e-mail, letter) to understand the primary reason for the participant's decision to withdraw their consent/exercise data privacy rights and record this information. The Investigator shall clearly document if the participant has withdrawn his/her consent for the use of data in addition to study discontinuation.

Study treatment must be discontinued and no further assessments conducted, and the data that would have been collected at subsequent visits will be considered missing.

Further attempts to contact the participant are not allowed unless safety findings require communicating or follow-up.

If the participant agrees, a final evaluation at the time of the participant's withdrawal of consent/exercise of data privacy rights should be made as detailed in [Section 8](#).

Further details on withdrawal of consent or the exercise of participants' data privacy rights are included in the corresponding informed consent form.

9.3 Study completion and post-study treatment

Study completion is defined as when the last participant finishes their Study Completion visit and any repeat assessments associated with this visit have been documented and followed-up appropriately by the Investigator or, in the event of an early study termination decision, the date of that decision.

All treated participants should have a safety follow-up call conducted 30 days after last administration of study treatment. The information collected is kept as source documentation. All SAEs reported during this time period must be reported as described in [Section 10.1.3](#). Documentation of attempts to contact the participant should be recorded in the source documentation.

9.4 Early study termination by the sponsor

The study can be terminated by Novartis at any time.

Reasons for early termination

- Unexpected, significant, or unacceptable safety risk to participants enrolled in the study
- Decision based on recommendations from applicable board(s) after review of safety and efficacy data
- Discontinuation of study drug development

In taking the decision to terminate, Novartis will always consider participant welfare and safety. Should early termination be necessary, participants must be seen as soon as possible and treated as a participant who discontinued from study treatment: participants will complete an EOS visit. The investigator may be informed of additional procedures to be followed in order to ensure that adequate consideration is given to the protection of the participant's interests. The investigator or sponsor depending on local regulation will be responsible for informing IRBs/IECs of the early termination of the trial.

10 Safety monitoring and reporting

10.1 Definition of adverse events and reporting requirements

10.1.1 Adverse events

An AE is any untoward medical occurrence (e.g. any unfavorable and unintended sign [including abnormal laboratory findings], symptom or disease) in a clinical investigation participant after providing written informed consent for participation in the study. Therefore, an AE may or may not be temporally or causally associated with the use of a medicinal (investigational) product.

The investigator has the responsibility for managing the safety of individual participant and identifying AEs.

Novartis qualified medical personnel will be readily available to advise on trial related medical questions or problems.

The occurrence of AEs must be sought by non-directive questioning of the participant at each visit during the study. AEs also may be detected when they are volunteered by the participant during or between visits or through physical examination findings, laboratory test findings, or other assessments

AEs must be recorded under the signs, symptoms, or diagnosis associated with them, accompanied by the following information (as far as possible) (if the event is serious refer to [Section 10.1.2](#)):

1. The severity grade.

- mild: usually transient in nature and generally not interfering with normal activities
- moderate: sufficiently discomforting to interfere with normal activities
- severe: prevents normal activities

2. The causality

The investigator is obligated to assess the relationship between any treatment used in the study (study treatment) and each occurrence of each AE. The investigator will use clinical judgment to determine the relationship. A reasonable possibility of a relationship conveys that there are facts, evidence, and/or arguments to suggest a causal relationship, rather than a relationship cannot be ruled out. Alternative causes, such as underlying disease(s), concomitant therapy, and other risk factors, as well as the temporal relationship of the event to study intervention administration, will be considered and investigated. For causality assessment, the investigator will also consult the IB and/or product information, for marketed products.

The causality assessment is one of the criteria used when determining regulatory reporting requirements.

AE Reporting via an Electronic Data Collection Tool

The primary mechanism for reporting an AE to Novartis will be the electronic data collection tool.

If the electronic system is unavailable, then the site will use the paper AE data collection tool (see next section) to report the event.

The site will enter the AE data into the electronic system as soon as it becomes available.

After the study is completed at a given site, the electronic data collection tool will be taken offline to prevent the entry of new data or changes to existing data.

If a site receives a report of a new AE from a study participant or receives updated data on a previously reported AE after the electronic data collection tool has been taken offline, then the site can report this information on a paper AE form (see next section) or by telephone.

AE Reporting via Paper Data Collection Tool

Facsimile transmission of the AE paper data collection tool is the preferred method to transmit this information to Novartis.

In rare circumstances and in the absence of facsimile equipment, notification by telephone is acceptable with a copy of the AE data collection tool sent by overnight mail or courier service.

Initial notification via telephone does not replace the need for the investigator to complete and sign the AE data collection tool within the designated reporting timeframes.

10.1.2 Serious adverse events

An SAE is defined as any AE [appearance of (or worsening of any pre-existing)] undesirable sign(s), symptom(s), or medical condition(s) which meets any one of the following criteria:

- fatal
- life-threatening

Life-threatening in the context of a SAE refers to a reaction in which the participant was at risk of death at the time of the reaction; it does not refer to a reaction that hypothetically might have caused death if it were more severe (please refer to the ICH-E2D Guidelines).

- results in persistent or significant disability/incapacity
- constitutes a congenital anomaly/birth defect
- requires inpatient hospitalization or prolongation of existing hospitalization, unless hospitalization is for:
 - routine treatment or monitoring of the studied indication, not associated with any deterioration in condition
 - elective or pre-planned treatment for a pre-existing condition that is unrelated to the indication under study and has not worsened since signing the informed consent
 - social reasons and respite care in the absence of any deterioration in the participant's general condition
 - treatment on an emergency outpatient basis for an event not fulfilling any of the definitions of a SAE given above and not resulting in hospital admission
- is medically significant, e.g. defined as an event that jeopardizes the participant or may require medical or surgical intervention to prevent one of the outcomes listed above

Medical and scientific judgment should be exercised in deciding whether other situations should be considered serious reactions, such as important medical events that might not be immediately life threatening or result in death or hospitalization but might jeopardize the participant or might require intervention to prevent one of the other outcomes listed above. Such events should be considered as “medically significant.” Examples of such events are intensive treatment in an emergency room or at home for allergic bronchospasm, blood dyscrasias, or convulsions that do not result in hospitalization or development of dependency or abuse (please refer to the ICH-E2D Guidelines).

All new malignant neoplasms will be assessed as serious under “medically significant” if other seriousness criteria are not met.

Any suspected transmission via a medicinal product of an infectious agent is also considered a SAE.

All reports of intentional misuse and abuse of the product are also considered SAE irrespective if a clinical event has occurred.

10.1.3 SAE reporting

To ensure participant safety, every SAE, regardless of causality, occurring after the participant has provided informed consent and until 8 weeks after the last administration of study treatment must be reported to Novartis safety within 24 hours of learning of its occurrence. Detailed instructions regarding the submission process and requirements are to be found in the investigator folder provided to each site.

All follow-up information for the SAE including information on complications, progression of the initial SAE and recurrent episodes must be reported as follow-up to the original episode within 24 hours of the investigator receiving the follow-up information. An SAE occurring at a different time interval or otherwise considered completely unrelated to a previously reported one must be reported separately as a new event.

If the SAE is not previously documented in the Investigator’s Brochure or Package Insert (new occurrence) and is thought to be related to the study treatment, a CMO & PS Department associate may urgently require further information from the investigator for health authority reporting. Novartis may need to issue an Investigator Notification (IN) to inform all investigators involved in any study with the same study treatment that this SAE has been reported.

Suspected Unexpected Serious Adverse Reactions (SUSARs) will be collected and reported to the competent authorities and relevant ethics committees in accordance with EU Guidance 2011/C 172/01 or as per national regulatory requirements in participating countries.

Any SAEs experienced after 8 weeks after the last administration of study treatment should only be reported to Novartis Safety if the investigator suspects a causal relationship to study treatment.

SAE Reporting via an Electronic Data Collection Tool

The primary mechanism for reporting an SAE to Novartis will be the electronic data collection tool.

If the electronic system is unavailable, then the site will use the paper SAE data collection tool (see next section) to report the event within 24 hours.

The site will enter the SAE data into the electronic system as soon as it becomes available.

After the study is completed at a given site, the electronic data collection tool will be taken offline to prevent the entry of new data or changes to existing data.

If a site receives a report of a new SAE from a study participant or receives updated data on a previously reported SAE after the electronic data collection tool has been taken offline, then the site can report this information on a paper SAE form (see next section) or by telephone.

SAE Reporting via Paper Data Collection Tool

Facsimile transmission of the SAE paper data collection tool is the preferred method to transmit this information to Novartis.

In rare circumstances and in the absence of facsimile equipment, notification by telephone is acceptable with a copy of the SAE data collection tool sent by overnight mail or courier service.

Initial notification via telephone does not replace the need for the investigator to complete and sign the SAE data collection tool within the designated reporting timeframes.

10.1.4 Pregnancy reporting

If a female trial participant becomes pregnant, the study treatment should be stopped, and the pregnancy consent form should be presented to the trial participant. The participants must be given adequate time to read, review and sign the pregnancy consent form. This consent form is necessary to allow the investigator to collect and report information regarding the pregnancy. To ensure participant safety, each pregnancy occurring after signing the informed consent must be reported to Novartis within 24 hours of learning of its occurrence. The pregnancy should be followed up to determine outcome, including spontaneous or voluntary termination, details of the birth, and the presence or absence of any birth defects, congenital abnormalities, or maternal and/or newborn complications.

Pregnancy should be recorded and reported by the investigator to the Novartis Chief Medical Office and Patient Safety (CMO&PS). Pregnancy follow-up should be recorded on the same form and should include an assessment of the possible relationship to the study treatment any pregnancy outcome. Any SAE experienced during pregnancy must be reported.

10.1.5 Reporting of study treatment errors including misuse/abuse

Medication errors are unintentional errors in the prescribing, dispensing, administration or monitoring of a medicine while under the control of a healthcare professional, participant or consumer (EMA definition).

Misuse refers to situations where the medicinal product is intentionally and inappropriately used not in accordance with the protocol.

Abuse corresponds to the persistent or sporadic, intentional excessive use of a medicinal product, which is accompanied by harmful physical or psychological effects.

Study treatment errors and uses outside of what is foreseen in the protocol will be recorded on the appropriate CRF irrespective of whether or not associated with an AE/SAE and reported to Safety only if associated with an SAE. Misuse or abuse will be collected and reported in the safety database irrespective of it being associated with an AE/SAE within 24 hours of Investigator's awareness.

Table 10-1 **Guidance for capturing the study treatment errors including misuse/abuse**

Treatment error type	Document in Dosing CRF (Yes/No)	Document in AE eCRF	Complete SAE form
Unintentional study treatment error	Yes	Only if associated with an AE	Only if associated with an SAE
Misuse/Abuse	Yes	Yes	Yes, even if not associated with a SAE

For more information on AE and SAE definition and reporting requirements, please see the respective sections.

10.2 Additional Safety Monitoring

10.2.1 Liver safety monitoring

To ensure participant safety and enhance reliability in determining the hepatotoxic potential of an investigational drug, a standardized process for identification, monitoring and evaluation of liver events has to be followed.

Please refer to [Table 16-1](#) in [Section 16.2](#) for complete definitions of liver laboratory triggers.

Once a participant is exposed to study treatment, every liver event defined in [Table 16-1](#) should be followed up by the investigator or designated personnel at the trial site, as summarized below. Additional details on actions required in case of liver events are outlined in [Table 16-2](#).

- Repeat liver chemistry tests (i.e., ALT, AST, TBL, PT/INR, ALP and G-GT) to confirm elevation. These liver chemistry repeats will be performed using the central laboratory. If results will not be available from the central laboratory, then the repeats can also be performed at a local laboratory to monitor the safety of the participant. If a liver event is subsequently reported, any local liver chemistry tests previously conducted that are associated with this event should have results recorded on the appropriate CRF. If the

initial elevation is confirmed, close observation of the participant will be initiated, including consideration of treatment interruption if deemed appropriate.

- Discontinuation of the investigational drug (refer to the Discontinuation of study treatment section), if appropriate
- Hospitalization of the participant if appropriate
- Causality assessment of the liver event
- Thorough follow-up of the liver event should include
- These investigations can include based on investigator's discretion: serology tests, imaging and pathology assessments, hepatologist's consultancy; obtaining more detailed history of symptoms and prior or concurrent diseases, history of concomitant drug use, exclusion of underlying liver disease

All follow-up information and procedures performed must be recorded as appropriate in the CRF.

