16.2 Appendix 2: Liver event and laboratory trigger definitions & follow-up requirements

Table 16-1 Liver event and laboratory trigger definitions

	Definition/ threshold
Liver laboratory triggers If ALT, AST and total bilirubin normal at baseline:	
 • ALT or AST > 5 × ULN • ALP > 2 × ULN (in the absence of known bone pathology) • Total bilirubin > 3 × ULN (in the absence of known Gilbert syndrome) • ALT or AST > 3 × ULN and INR > 1.5 • Potential Hy's Law cases (defined as ALT or AST > 3 × ULN and Total bilirubin > 2 × ULN [mainly conjugated fraction] without notable increase in ALP to > 2 × ULN) • Any clinical event of jaundice (or equivalent term) • ALT or AST > 3 × ULN accompanied by (general) malaise, fatigue, abdominal pain, nausea, or vomiting, or rash with eosinophilia • Any AE potentially indicative of a liver toxicity
If ALT or AST abnormal at baseline:	
 • ALT or AST > 3x baseline or > 300 U/L (whichever occurs first)

Table 16-2 Follow up requirements for liver laboratory triggers – ALT, AST, TBL

ALT	TBL	Liver Symptoms	Action
ALT increase without bilirubin increase:			
If normal at baseline: ALT > 3 x ULN	Normal	None	
● No change to study treatment● Measure ALT, AST, ALP, GGT, TBIL, INR, albumin, CK, and GLDH in 48-72 hours.● Follow-up for symptoms.
If elevated at baseline: ALT > 2 x baseline or > 300 U/L (whichever occurs first)	For participants with Gilbert's syndrome: No change in baseline TBL		
If normal at baseline: ALT > 5 x ULN for more than two weeks	Normal	None	
● Interrupt study drug● Measure ALT, AST, ALP, GGT, TBIL, INR, albumin, CK, and GLDH in 48-72 hours.● Follow-up for symptoms.● Initiate close monitoring and workup for competing etiologies.● Study drug can be restarted only if another etiology is identified and liver enzymes return to baseline.
If elevated at baseline: ALT > 3 x baseline or > 300 U/L (whichever occurs first) for more than two weeks	For participants with Gilbert's syndrome: No change in baseline TBL		
If normal at baseline: ALT > 8 x ULN	Normal	None	
ALT increase with bilirubin increase:			
If normal at baseline: ALT > 3 x ULN	TBL > 2 x ULN (or INR > 1.5)	None	
If elevated at baseline: ALT > 2 x baseline or > 300 U/L (whichever occurs first)	For participants with Gilbert's syndrome: Doubling of direct bilirubin		

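### An AST-led potential Hy's Law case is a liver event in Table 16-1 but meets no Table 16-2 condition when ALT is at or below 3 × ULN, so interruption and restart rest on judgment

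*Protocol*

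**What the plan says.** Section 10.2.1 sets a standardized process for every liver event defined in Table 16-1. It asks for repeat chemistry and, if the elevation is confirmed, close observation, "including consideration of treatment interruption if deemed appropriate". It also asks for discontinuation or hospitalization where appropriate, and a causality assessment. For the actions themselves it says "Additional details on actions required in case of liver events are outlined in" Table 16-2.

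In Appendix 2, Table 16-1 lists the triggers that apply when ALT, AST and total bilirubin are normal at baseline. One is "ALT or AST > 3 × ULN and INR > 1.5". Another is potential Hy's Law, "defined as ALT or AST > 3 × ULN and Total bilirubin > 2 × ULN", with mainly conjugated bilirubin and ALP not above 2 × ULN. If ALT or AST was abnormal at baseline, the one trigger is "ALT or AST > 3x baseline or > 300 U/L (whichever occurs first").

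The caption of Table 16-2 names ALT, AST and bilirubin, but no row gives an AST threshold. Under "ALT increase with bilirubin increase" the enzyme condition is ALT > 3 × ULN for a normal baseline, or ALT > 2 × baseline or > 300 U/L for an elevated one. It is paired with "TBL > 2 x ULN (or INR > 1.5"). The interruption action includes nine analytes to repeat in 48-72 hours, a work-up for competing causes, and this rule: "Study drug can be restarted only if another etiology is identified and liver enzymes return to baseline".

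**The concern.** The protocol's own definition of its most serious laboratory liver event treats ALT and AST alike. The table that turns the event into an instruction does not. Two participants with the same bilirubin can both be potential Hy's Law cases, yet only the one whose ALT crosses the threshold has a required interruption.

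The difference carries over to restarting. Section 6.6 lets dosing resume at the next scheduled visit once the safety risk has resolved. Table 16-2 also requires that another cause be found and that enzymes be back at baseline.

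An AST rise is foreseeable in this population, because Section 8.4.4 lists raised aspartate transaminase among the features of macrophage activation syndrome (MAS). Although enrollment was stopped, dosing continues every 4 weeks until approval and commercial availability, or until the sponsor ends the study (Sections 3 and 6.1.5). At stake is participant safety, not the analysis.

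**Working it through.** No sample size, power or error rate is involved. The check compares the rules for a participant with normal baseline tests, AST > 3 × ULN and ALT ≤ 3 × ULN.

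**Step 1. Which Table 16-2 conditions can be met?** The table has 2 (no change to treatment) + 3 (higher or sustained ALT) + 2 (bilirubin/INR) + 2 (symptoms) = 9 conditions, all on ALT. Five apply to a normal baseline: ALT > 3 × ULN alone; > 5 × ULN for more than two weeks; > 8 × ULN; > 3 × ULN with bilirubin or INR raised; > 3 × ULN with symptoms. The lowest threshold is 3 × ULN, so ALT ≤ 3 × ULN meets 0 of 5.

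**Step 2. Illustrative cases** (normal baseline, values in multiples of ULN except INR; bilirubin in case a taken as mainly conjugated).

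| Case | AST | ALT | Bilirubin | Other | Table 16-1 event? | Table 16-2 condition met? |
|---|---|---|---|---|---|---|
| a | 4 | 2.5 | 2.5 | ALP 1.5 | Yes, potential Hy's Law | None |
| b | > 5 | 2.5 | normal | INR 1.8 | Yes, AST alone and AST with INR | None |
| c | 4 | 2.5 | 4 | – | Yes, bilirubin > 3 in any case | None |
| d | 4 | 3.5 | 2.5 | – | Yes, if the conjugated-fraction and ALP conditions hold | Yes, bilirubin/INR condition |

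Case d shows that the gap closes once ALT passes 3 × ULN.

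**Step 3. How is the INR case reached?** Table 8-2 measures PT/INR only when there is a liver event. AST at 4 × ULN with normal bilirubin and no other trigger is not such an event, because the AST-alone trigger is > 5 × ULN. No INR would be drawn under the protocol. The INR case therefore follows another trigger: AST > 5 × ULN, ALP > 2 × ULN, bilirubin > 3 × ULN, jaundice, symptoms or a liver adverse event. Bilirubin is in the chemistry panel without that restriction, so case a needs no earlier trigger.

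**Step 4. Does Table 16-3 fill the gap?** Its bilirubin rows are for isolated elevation, which these cases are not. If a site used them anyway, case c (> 3 to 10 × ULN) would be interrupted, but case a (> 1.5 to 3.0 × ULN) would be told to maintain treatment. Case b has normal bilirubin and matches no bilirubin row. On either reading, bilirubin > 2 to 3 × ULN, and INR > 1.5 with bilirubin ≤ 3 × ULN, have no ordered interruption.

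**Step 5. What still applies?** Section 10.2.1: repeat tests, observation if confirmed, causality. Appendix 1: sponsor notification for AST > 3 × ULN, alone or with bilirubin > 2 × ULN. Section 6.6, Section 9.1.1 and the last row of Table 16-3: interruption or discontinuation, depending on how the investigator assesses the risk.

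**The case against.** The strongest reply is that these participants are already protected. Section 9.1.1 makes discontinuation mandatory wherever continued participation might put the participant at risk, the sponsor is notified at the same time as the investigator, and a 4-week dosing interval normally leaves time to retest. This stands as far as it goes. A reader might infer that an AST-led case is unmanaged, and the documents do not support that. What remains is that the investigator decides whether Section 9.1.1 applies, whereas for the same pattern led by ALT the protocol sets a threshold.

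Three further objections narrow the point:

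- **The table is damaged.** The action cell beside the bilirubin/INR conditions is blank in the extracted text. It looks like a merged cell, but that is an inference.
- **The INR case is indirect**, as Step 3 shows.
- **The abnormal-baseline trigger is not a third instance.** A reader might count it as one, but in Table 16-1 it has no bilirubin or INR component.

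It can also be said that ALT-only rows were deliberate, since aminotransferase abnormality is part of the disease (Appendix 3). That is a fair reason to leave the isolated-rise rows alone. It is less convincing for the bilirubin/INR rows, because the caption, both combined triggers and Appendix 1 all name AST. The symptom conditions have the same ALT-only wording although their trigger names AST. Leaving them out is a limit of scope, not a claim that they are consistent.

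**Conclusion.** The mismatch is real but narrow. For a normal baseline, an AST-led potential Hy's Law event, or AST > 3 × ULN with INR > 1.5, has no matching Table 16-2 condition while ALT is ≤ 3 × ULN. Four things are then not required by threshold: interruption, the 48-72 hour retest, the work-up for competing causes, and the strict restart rule.

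This assumes that the blank action cell carries the interruption instruction, and that the isolated-bilirubin heading of Table 16-3 is read literally. If a site applied Table 16-3 anyway, bilirubin above 3 × ULN would be covered.

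A reader might also infer that the protocol tells sites to keep dosing in a Hy's Law case. It does not: the maintain-treatment row is confined to isolated bilirubin elevation, although it could be misapplied.

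Severity is minor to moderate. The documents give no rate for such events, SAP Section 2.5.6 refers to 14 participants, and no endpoint or planned analysis is affected. Confidence is medium because of the unverified cell.

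**What to change.** In Table 16-2, change only the bilirubin/INR block and keep its bilirubin/INR column and action:

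- Sub-heading: *ALT or AST increase with bilirubin increase*.
- Normal-baseline condition: *ALT or AST > 3 × ULN (enzyme normal at baseline)*.
- Elevated-baseline condition: keep the ALT wording and add *or, if AST elevated at baseline: AST > 3 × baseline or > 300 U/L (whichever occurs first)*. This matches Table 16-1. Extending the ALT figure of 2 × baseline to AST would order interruption below the AST event threshold.
- State that each enzyme is judged against its own baseline, so that a participant with normal ALT and raised AST at entry is unambiguous.

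In Section 10.2.1, point to Tables 16-2 and 16-3 for the actions.

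The cost is two condition cells, one sub-heading and one cross-reference. They could go into the next amendment, with ethics committee approval and health authority approval where required (Section 14.1). No new tests are needed: all nine analytes in the Table 16-2 action are already in Table 8-2. The downside is an occasional interruption for an AST and bilirubin rise caused by the disease or by MAS, in patients for whom worsening disease is itself a risk. The existing restart rule allows dosing to resume once that cause is identified and enzymes are back at baseline.
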